Regardless of the delivery system, standards for SRS have to be followed according to AAPM guidelines. Commissioning of any SRS delivery system is well defined in accordance with AAPM guidelines. The biological effect is the same regardless of the technology such that radiation induces DNA damage leading to cell kill. SRS, whether single fraction or multi-fractions (up to 5 fractions), is a standard radiotherapeutic application for brain metastases. Acute side effects consist of radiation-induced edema that may require use of dexamethasone and manifests typically as headache, nausea, vomiting. Rarely are more serious side effects observed which can consist of obstructive hydrocephalus (<1%). The most significant late side effect consists of radiation necrosis and asymptomatic radiographic necrosis can occur in 10-20% of patients with symptomatic radiation necrosis in <10% of patients. Radiation necrosis represents an inflammatory reaction of the radiated tissue and can mimic tumour progression. Typically is the patient experiences headache, nausea and vomiting then dexamethasone is the primary treatment, rarely if neurologic deficit the surgery may be required. Typically radiation necrosis resolves with use of dexamethasone and confirmatory MRI scans are required to show stability or regression as opposed to progression. With well-defined normal tissue guidelines for dose limits, damage to other sensitive tissues in the brain such as the optic structures and brainstem is extremely rare. Precise pre-treatment planning is necessary to avoid damage to these organs at risk, and the dose limits proposed in this trial represents well defined standards for safe practice.

ADMIN UPDATE #1: 2017-OCT-03; AMEND #1: 2018-APR-06; AMEND #2: 2018-OCT-26

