*Partial Response (PR)*: at least a 30% decrease in the sum of measures (longest diameter for tumour lesions and short axis measure for nodes) of target lesions, taking as reference the baseline sum of diameters. Non target lesions must be non-PD. Confirmation of response is required in non-randomized studies.

*Stable Disease (SD)*: Neither sufficient shrinkage to qualify for PR nor sufficient increase to qualify for PD taking as reference the smallest sum of diameters on study.

Progressive Disease (PD): at least a 20% increase in the sum of diameters of measured lesions taking as references the smallest sum of diameters recorded on study (including baseline) AND an absolute increase of  $\geq 5\text{mm}$ . Appearance of new lesions will also constitute progressive disease (including lesions in previously unassessed areas). In exceptional circumstances, unequivocal progression of non-target disease may be accepted as evidence of disease progression, where the overall tumour burden has increased sufficiently to merit discontinuation of treatment or where the tumour burden appears to have increased by at least 73% in volume. Modest increases in the size of one or more non-target lesions are NOT considered unequivocal progression. If the evidence of PD is equivocal (target or non-target), treatment may continue until the next assessment, but if confirmed, the earlier date must be used.

A single CNS lesion must increase by an absolute value of  $\geq 5\text{ mm}$  to be considered progression.

Radiation Necrosis versus Progressive Disease: Progression is not unequivocal if change in imaging is possibly due to radiation necrosis. If the treated lesion changes in such a way that radiation necrosis is suspected then follow-up scans are required. If no further growth or regression is observed then the response assessment should be stable disease rather than progressive disease. If a patient has surgery and pathology indicates radiation necrosis then this should be noted in the response assessment. For SRS treated lesions, an advanced imaging modality such as perfusion MR imaging, MR spectroscopy, or 18FLT or 18FDG positron emission tomography (PET) may be used as additional evidence of tumor progression or treatment effect/radionecrosis.

Corticosteroid Use and Clinical Deterioration:

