- a. An increase in corticosteroid dose alone, in the absence of clinical deterioration related to tumour, will not be used as a sole determinant of progression. Patients with stable imaging studies whose corticosteroid dose was increased for reasons other than clinical deterioration related to tumour do not qualify for stable disease or progression. They should be observed closely. If their corticosteroid dose can be reduced back to baseline, they will be considered as having stable disease; if further clinical deterioration related to tumour becomes apparent, they will be considered to have progression.
- b. The definition of clinical deterioration is left to the discretion of the treating physician, but it is recommended that a decline in the KPS from 100 or 90 to 70 or less, a decline in KPS of at least 20 points from 80 or less, or a decline in KPS from any baseline to 50 or less, for at least 7 days, be considered neurologic deterioration unless attributable to comorbid events, treatment-related toxicity, or changes in corticosteroid dose.

Table 1: Integration of Target, non-Target and New Lesions into Response Assessment:

Target Lesions	Non-Target Lesions	New Lesions	Overall Response	Best Response for this Category also Requires
Target lesions ± non target lesions				
CR	CR	No	CR	tumour nodes <10mm
CR	Non-CR/Non-PD	No	PR	
CR	Not all evaluated	No	PR	
PR	Non-PD/ not all evaluated	No	PR	
SD	Non-PD/ not all evaluated	No	SD	documented at least once $\geq$ 4 wks. from baseline
Not all evaluated	Non-PD	No	NE	
PD	Any	Any	PD	
Any	PD	Any	PD	
Any	Any	Yes	PD	
Non target lesions ONLY				
No Target	CR	No	CR	tumour nodes < 10mm
No Target	Non-CR/non-PD	No	Non-CR/non-PD	
No Target	Not all evaluated	No	NE	
No Target	Unequivocal PD	Any	PD	
No Target	Any	Yes	PD	
Note: Patients with a global deterioration of health status requiring discontinuation of treatment without objective evidence of disease progression at that time should be reported as "symptomatic deterioration". This is a reason for stopping therapy, but is NOT objective PD. Every effort should be made to document the objective progression even after discontinuation of treatment.				

For non-randomized trials, where confirmation of response is required, best overall response can be interpreted as follows:

Response: First Time Point	Subsequent Time Point	BEST Overall Response	Also Requires
CR	CR	CR	tumour nodes < 10mm
CR	PR	SD, PD or PR (see comment*)	

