CR	SD	SD provided minimum criteria for SD duration met, otherwise, PD	
CR	PD	SD provided minimum criteria for SD duration met, otherwise, PD	
CR	NE	SD provided minimum criteria for SD duration met, otherwise NE	
PR	CR	PR	
PR	PR	PR	
PR	SD	SD	
PR	PD	SD provided minimum criteria for SD duration met, otherwise, PD	
PR	NE	SD provided minimum criteria for SD duration met, otherwise NE	
NE	NE	NE	

\* may consider PR providing initial "CR" likely PR on subsequent review – then original CR should be corrected.  
Recurrence of lesion after true CR is PD.

Because CNS progression of disease may be masked by corticosteroids or manifest by neurological deterioration without radiological progression, the following ADDITIONAL parameters will be used:

Response Criteria for CNS Metastases

Criterion	CR	PR	SD	PD
Target lesions	None	$\geq 30\%$ decrease in sum LD relative to baseline	< 30% decrease relative to baseline but < 20% increase in sum LD relative to nadir	$\geq 20\%$ increase in sum LD relative to nadir*
Non-target lesions	None	Stable or improved	Stable or improved	Unequivocal PD*
New lesion(s)**	None	None	None	Present*
Corticosteroids	None	Stable or decreased	Stable or decreased	NA +
Clinical status	Stable or improved	Stable or improved	Stable or improved	Worse*
Requirement for response	All	All	All	Any +

\* Progression occurs when this criterion is met.

\*\* New lesion = new lesion not present on prior scans and visible in at least 2 projections. If a new lesion is equivocal, for example because of its small size, continued therapy may be considered, and follow up evaluation will clarify if it represents truly new disease. If repeat scans confirm there is definitely a new lesion, then progression should be declared using the date of the initial scan showing the new lesion. For immunotherapy-based approaches, new lesions alone to do not define progression (See "Guidance in the case of new lesion(s) while on immunotherapy").

+ Increase in corticosteroids alone will not be taken into account in determining progression in the absence of persistent clinical deterioration.

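### The radiation-necrosis rule names only stable disease, which contradicts the PR and SD definitions when the sum is still at least 30% below baseline, and no precedence is stated

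*Combined protocol and SAP*

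**What the plan says.** The necrosis rule appears in Section 7.3.15 and again in Section 8.2.5. It starts from suspicion and asks for more imaging: "If the treated lesion changes in such a way that radiation necrosis is suspected then follow-up scans are required". It then assigns the category: "If no further growth or regression is observed then the response assessment should be stable disease rather than progressive disease". Neither place mentions PR.

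The other definitions in Section 8.2.5 use two reference points:

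- PR requires "at least a 30% decrease in the sum of measures", with the baseline sum as reference.
- PD requires "at least a 20% increase in the sum of diameters of measured lesions taking as references the smallest sum of diameters recorded on study", together with an absolute increase of at least 5 mm.
- SD is "Neither sufficient shrinkage to qualify for PR nor sufficient increase to qualify for PD".
- The table of response criteria for CNS metastases limits SD on target lesions to "< 30% decrease relative to baseline but < 20% increase in sum LD relative to nadir". Its PR column also requires stable or decreased corticosteroids and a stable or improved clinical status.

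Response must be confirmed. The confirmation table is introduced by "For non-randomized trials, where confirmation of response is required, best overall response can be interpreted as follows". It turns PR followed by SD into a best response of SD, and PR followed by PR into PR. Best response is taken over the whole treatment period. The primary endpoint (Section 12.2) is the objective response rate in the brain.

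**The concern.** PD is measured from nadir and PR from baseline, so one scan can meet both thresholds. Once PD has been set aside as probable necrosis, the PR definition may still be met, but the necrosis rule names SD. Two readers applying this protocol in good faith could code the same scan PR or SD.

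If that scan is the one that should confirm a first PR, the choice decides whether the patient counts as a responder. Section 7.0 has all lesions treated with SRS in both cohorts, so the rule can reach any CNS target lesion. Section 11.1 has both local and central radiology results reported, so both sets of readers need the same rule. The trial is single-arm and is decided on a count of responders out of 46, where a few patients can change the conclusion.

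**Working it through.** **1. Can one scan meet both PD and PR?** Let B be the baseline sum, N the nadir and S the current sum.

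- PD by target sum: S ≥ 1.20 × N and S − N ≥ 5 mm.
- PR: S ≤ 0.70 × B.
- Both together need 1.20 × N ≤ 0.70 × B, so N ≤ (0.70/1.20) × B = 0.583 × B. The nadir must be at least 41.7% below baseline.

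Example: B = 40 mm, N = 22 mm, S = 27.5 mm.

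- Nadir against baseline: 22/40 = 0.55, a 45% decrease (PR).
- Current against nadir: 27.5/22 = 1.25 and 27.5 − 22 = 5.5 mm (PD thresholds met).
- Current against baseline: 27.5/40 = 0.6875, a 31% decrease (PR threshold still met).

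If follow-up scans then show no change, the necrosis rule gives SD. The SD definition and the CNS table both rule SD out at a 31% decrease.

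Two limits follow. On the first post-baseline scan the smallest sum is the baseline itself, so PD by sum would mean S ≥ 1.20 × B, which cannot also be ≤ 0.70 × B; the overlap cannot occur there. With small sums the 5 mm condition binds: for B = 20 mm, PR needs S ≤ 14 mm, so N must be 9 mm or less.

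There is a second route. The rule is triggered by a change in a treated lesion, so suspected necrosis in a non-target lesion could invoke it while the target sum stays in the PR range.

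**2. When does it change best response?**

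| Sequence | Best response if the necrosis scan is coded SD | If it is coded PR |
|---|---|---|
| First PR, then necrosis scan | SD | PR |
| PR, PR, then necrosis scan | PR (already confirmed) | PR |
| First PR, necrosis scan, later PR | Not stated | PR |

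Only the first and third rows matter. The width of the window is itself unclear. Footnote 10 of the Section 5.0 flowsheet asks for repeat scans after 4 weeks to confirm a CR or PR, but its marker sits only in the post-therapy column. Imaging on treatment is every 8 weeks, ±14 days.

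**3. The plan's design figure.** Section 12.3 gives p0 = 0.40, p1 = 0.60, alpha = beta = 0.10, more than 7/18 in the first stage and 22/46 in the second. With X1 the responders among the first 18 and X2 those among the next 28:

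P(success | p) = Σ over x = 8 to 18 of P(X1 = x) × P(X2 > 22 − x)

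Reading 22/46 as more than 22 responders gives alpha = 0.095 and power = 0.900, which reproduces the stated error rates. Reading it as 22 or more gives alpha = 0.144, above the stated 0.10.

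**4. What a loss of responders would do.** The documents give no rate for this event. The same formula, at assumed recorded response rates when the true rate is 60%:

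| Recorded rate | Power |
|---|---|
| 60% | 0.900 |
| 59.25% | 0.883 |
| 58.5% | 0.864 |

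The 58.5% row corresponds to 0.10 × 0.60 × 0.25 = 0.015: 10% necrosis (the low end of Section 3.4, which says "asymptomatic radiographic necrosis can occur in 10-20% of patients"), an assumed 60% of those patients responding, and an assumed 25% of cases falling in the critical window. The 59.25% row uses 5%, the low end of the range in Section 2.0: 0.05 × 0.60 × 0.25 = 0.0075. Neither product applies the overlap condition from step 1, which would reduce the loss further by the target-sum route.

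**The case against.** The strongest objection is that the necrosis sentence contrasts SD with PD and is silent on PR. Read together with the SD definition and the CNS table, a scan at least 30% below baseline cannot be SD, so a careful reader would code PR. This stands to the extent that a reader who infers that the plan forces a downgrade goes too far: what the documents show is a contradiction without stated precedence. It does not remove the need for a rule, because the sentence is directive and appears twice.

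Three further points stand and limit the size:

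- If responders are rescanned at 4 weeks, many PRs will be confirmed before any swelling, and a confirmed PR is safe.
- Section 3.4 calls necrosis a late effect and says that symptomatic cases are treated with dexamethasone. Patients whose corticosteroids increase or whose clinical status worsens fail the CNS criteria for PR whatever the necrosis sentence says.
- The phrase about growth or regression can be read as neither growth nor regression. On that reading a lesion that later shrinks falls outside the rule and later scans can be scored PR.

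A reader might also infer a large loss. Taking 20% necrosis, 60% responders and 50% of cases in the window gives 0.20 × 0.60 × 0.50 = 6 points, a recorded rate of 54% and power of 0.70. The arithmetic is right but the documents do not support the inputs. It stacks upper values, ignores the overlap condition, sits badly with a late effect, and sets aside the 5-10% also given in Section 2.0.

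**Conclusion.** The concern holds as an unresolved contradiction in how the primary endpoint is scored. When suspected progression is set aside as necrosis and the sum is still at least 30% below baseline, the necrosis rule says SD while the PR and SD definitions and the CNS table say PR, provided the other CNS criteria for PR are met.

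The affected group is narrow. By target sum it needs the deep nadir and the absolute growth derived above, and best response changes only when PR is not yet confirmed. Under the literal reading the bias is towards a lower intracranial response rate, so it cannot of itself produce a false positive result. Its size cannot be found from the documents and is probably small. The fall in power to 0.86 is an illustration resting on the assumed responder and timing shares, not an estimate.

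It would also go too far to describe each affected scan as a true PR that has been lost: the rule concerns suspected necrosis, and the other CNS criteria still have to be met. The point is nevertheless worth correcting before responses are read, because it is a stated rule that can give the wrong category and the correction is cheap.

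**What to change.** In Sections 8.2.5 and 7.3.15, replace the sentence that assigns SD with a rule along these lines: if follow-up scans do not support progression, the time point is not PD; its category is set by the measured sum against baseline, PR if the sum is at least 30% below baseline and all other CNS criteria for PR are met, otherwise SD.

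Add one sentence on confirmation: whether such a time point can confirm an earlier PR, and how PR, then SD, then PR is handled. Flag these time points in the data and report the intracranial response rate with and without them, for both local and central readings.

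The cost is a few sentences and one sensitivity line, using measurements already collected. The drawback is that a few borderline cases will count as PR; the sensitivity line shows how many and whether they matter.

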8.3 Response Duration

Response duration will be measured from the time measurement criteria for CR/PR (whichever is first recorded) are first met until the first date that recurrent or progressive disease is objectively documented, taking as reference the smallest measurements recorded on study (including baseline).

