## 8.0 CRITERIA FOR MEASUREMENT OF STUDY ENDPOINTS

### 8.1 Definitions

*Response Assessments:* The following algorithms will be used to support primary and secondary efficacy endpoints in the present trial.

*CNS Assessments:* For efficacy assessment in the CNS to support the primary endpoint of intracranial response, a protocol defined RECIST 1.1-based approach will be utilized with modifications that reflect the approach of the RANO-BM Working Group. RECIST 1.1, uni-dimensional longest diameter (LD) measurements will be used with a lower limit of size for defining a measurable lesion,  $> 1$  cm based on the baseline MRI of brain. CNS lesions  $< 1$  cm are non-target lesions. Best overall CNS response represents a composite of radiographic CNS target and non-target response (see definitions below), corticosteroid use, and clinical status.

*Extracranial Disease Assessments:* Assessment of response of extracranial disease will use RECIST 1.1.

*Overall Response Assessments:* Overall response assessment will be assessed using RECIST 1.1. Overall response will be measured as the sum of the LD of CNS + extracranial index lesions. The size cut-off of a measurable lesion in the extracranial compartment will follow the RECIST 1.1 definition of 1.0 cm.

- 8.1.1 Evaluable for adverse events. All patients will be evaluable for adverse event evaluation from the time of their first treatment.
- 8.1.2 Evaluable for response. All patients who have received at least one cycle of therapy and have their disease re-evaluated will be considered evaluable for response (exceptions will be those who exhibit objective disease progression prior to the end of cycle 1 who will also be considered evaluable). Patients on therapy for at least this period and who meet the other listed criteria will have their response classified according to the definitions set out below [Eisenhauer 2009].

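### Section 8.3 dates response by tumour measurement and objective progression only, so intracranial response duration can start before, and run past, the composite CNS response it is meant to time

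*Combined protocol and SAP*

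**What the plan says.** Duration of response is a secondary endpoint (1.2 and 12.1), listed without naming a compartment. Section 8.3 is the only rule for dating it. The start is: "Response duration will be measured from the time measurement criteria for CR/PR (whichever is first recorded) are first met". The end is: "until the first date that recurrent or progressive disease is objectively documented". The reference for progression in that sentence is the smallest measurements on study.

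For the brain, 8.1 defines something wider: "Best overall CNS response represents a composite of radiographic CNS target and non-target response (see definitions below), corticosteroid use, and clinical status". The CNS response table in 8.2.5 puts this into effect, introduced by: "Because CNS progression of disease may be masked by corticosteroids or manifest by neurological deterioration without radiological progression, the following ADDITIONAL parameters will be used". In that table:

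- CR, PR and SD require all rows to be met. PR needs at least 30% shrinkage, no new lesion, stable or decreased corticosteroids, and stable or improved clinical status.
- PD requires any one marked row. Worse clinical status is marked, and the footnote reads: "Progression occurs when this criterion is met".
- A steroid increase by itself is not PD: "Increase in corticosteroids alone will not be taken into account in determining progression in the absence of persistent clinical deterioration". It does, however, prevent CR, PR and SD.

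Section 12.2 names plain RECIST v1.1 for response and does not mention the CNS modifications.

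**The concern.** The event that makes a patient an intracranial responder and the event that starts the duration clock are defined differently. So are the event that ends an intracranial response and the event that stops the clock. Two analysts could follow the protocol and report different durations for the same patient.

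Section 2.0 gives this endpoint weight. It cites intracranial response durations of 20.1 and 28.1 weeks for dabrafenib alone, judges them not significantly different from radiation alone, and offers longer duration as a reason for the combination. A dating rule that can err only upwards is undesirable for that purpose.

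The situations are foreseeable. Section 3.4 says oedema after radiosurgery may need dexamethasone and that radiation necrosis is treated with it. Performance status is recorded on day 1 of every 28-day cycle, but brain MRI only every 8 weeks, so clinical progression can be recorded between scans.

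**Working it through.** The plan states no figure for this point, so there is none to reproduce. The check compares the two rules and then illustrates the size.

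**1. Start of the clock.** The composite start requires the size criterion and the other rows. The literal 8.3 start requires the measurement criterion only. The 8.3 start is therefore earlier than or equal to the composite start, never later.

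*Example A (hypothetical).* Week 8: sum of diameters down 45%, dexamethasone above baseline for oedema, so not a CNS PR. Week 16: down 50%, dexamethasone back to baseline, first CNS PR. Week 24: confirmed. Week 40: new lesion.
- CNS table: 40 - 16 = 24 weeks.
- Literal 8.3: 40 - 8 = 32 weeks.

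**2. End of the clock.** The table ends the response at any PD criterion. Section 8.3 ends it at objectively documented progression. The note under Table 1 in 8.2.5 says that deterioration without objective evidence of progression is not objective PD. The 8.3 end is therefore later than or equal to the table's end.

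*Example B (hypothetical).* PR at week 8, confirmed at week 16, worse clinical status from tumour at week 20, measurable growth at week 32.
- CNS table: 20 - 8 = 12 weeks.
- Literal 8.3: 32 - 8 = 24 weeks.

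**3. Routes that do and do not matter at the start.**
- Raised corticosteroids at the first scan with 30% shrinkage: this delays CNS PR without being PD. It is the real route.
- Worse clinical status: this is itself PD, so such a patient is not waiting to become a responder. Only decline that is not persistent, or is attributed to comorbidity, toxicity or steroid change, leaves a narrow gap.
- The no-steroid condition for CR: a patient with no visible lesions on stable steroids already meets the PR row, and 8.3 takes whichever of CR or PR comes first. This does not by itself delay the start.

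**4. Size for an affected patient.** The start moves by one scan interval: nominally 8 weeks, or 4 to 12 weeks if both scans use the full 14-day window (8 - 4 to 8 + 4). For scale, 8/20.1 = 40% and 8/28.1 = 28% of the cited medians.

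**5. Size for the group (assumption only).** The share *s* of responders affected at the start is not in the documents. Assume exponential composite durations with median M, no censoring, and g = 8 weeks added for share *s*. With rate λ = ln 2 / M, the new median solves exp(-λm) × (1 - s + s·exp(gλ)) = 0.5, so the shift is ln(1 - s + s·exp(gλ)) / λ.

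| | M = 20.1 | M = 28.1 |
|---|---|---|
| λ per week | 0.03448 | 0.02467 |
| exp(8λ) | 1.3177 | 1.2182 |
| s = 0% | 0 | 0 |
| s = 10% | ln(1.0318)/λ = 0.91 weeks | ln(1.0218)/λ = 0.87 weeks |
| s = 20% | ln(1.0635)/λ = 1.79 weeks | ln(1.0436)/λ = 1.73 weeks |
| s = 30% | ln(1.0953)/λ = 2.64 weeks | ln(1.0654)/λ = 2.57 weeks |

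The mean shift is s × 8: 0.8, 1.6 and 2.4 weeks for 10%, 20% and 30%. Simulation of one million durations per median agrees to within 0.02 weeks. Any effect at the end of the clock would add to these figures; its frequency is not given either.

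**The case against.** **The wording can be read the other way.** Section 8.0 is headed as criteria for measuring study endpoints, so the measurement criteria in 8.3 might include the CNS table. That reading is possible. It is not the natural one: the same sentence refers to smallest measurements, and 8.4, next to it, uses the broader wording of criteria for progression. It also does not resolve the end date. What stands is that the text permits both readings.

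**The endpoint may not be intracranial.** No compartment is named, and 12.2 says RECIST v1.1, for which dating by measurement fits. This stands as a second ambiguity to settle, not as a defence of 8.3 for intracranial duration.

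**Affected patients may be few.** Prophylactic dexamethasone in 7.1.2 and 7.3.1 is brief, and radiosurgery begins 7 to 14 days after the drugs, so it should usually be over by the week 8 scan. This stands. Longer treatment for oedema is foreseen, but no frequency is given.

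**Example B may not be observed.** Section 10.3 does not require continued disease follow-up once a patient leaves treatment with progression, so a week 32 scan may not exist. It would arise mainly when treatment continues under 10.2, or when sites try to document objective progression afterwards, as 8.2.5 asks. This limits how often the end-date problem occurs.

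**A measurement-based duration is defensible.** Clinical deterioration is left to the treating physician, and central review in 11.1 covers imaging only. This is a real cost of composite dating and is reflected in the fix.

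**Conclusion.** The mismatch is real. Taken literally, 8.3 can start intracranial response duration before a CNS response exists and continue it past CNS progression as the protocol's own table defines it. Both departures lengthen the duration and neither can shorten it.

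The effect is conditional. It is zero for any patient who meets all criteria at the same scan and later progresses on imaging. For an affected patient it is nominally 8 weeks at the start, plus the gap from clinical to imaging progression at the end. The group effect cannot be derived from the documents. The shifts of about 0.9 weeks (10% affected) and 1.7-1.8 weeks (20%) rest on assumed shares, exponential durations and no censoring.

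Three stronger readings are tempting but unsupported:

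- *That the reported duration will be overstated.* The share affected is unknown and could be nil.
- *That the comparison with 20.1 and 28.1 weeks is biased.* The documents do not show how those durations were dated.
- *That response duration will contradict intracranial PFS.* The protocol lists intracranial PFS but never defines it, so a conflict is inference.

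The primary intracranial response rate, the two-stage boundaries and the sample size do not depend on 8.3. This should be corrected as a secondary-endpoint definition; it does not threaten the trial's main conclusion.

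**What to change.** 1. In 8.3, state that intracranial response duration runs from the first assessment at which all CR or PR criteria of the CNS table are met (and later confirmed) to the first date on which any PD criterion of that table is met.
2. Keep the measurement-based rule for extracranial and overall response by RECIST 1.1, and say which durations will be reported.
3. In 12.2, replace the plain reference to RECIST v1.1 with the modified CNS criteria of 8.1 for intracranial response.
4. Report the imaging-only intracranial duration as a sensitivity analysis.

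The cost is small: a sentence in 8.3 and aligned wording in 12.2. Medication doses and dates (7.2.1) and performance status each cycle (Section 5.0) are already collected. There are two downsides. The reported intracranial duration may be slightly shorter, and dates set by clinical status rest on investigator judgement that central radiology review cannot check. The sensitivity analysis addresses the second.
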